7 STUDY SUBJECTS

7.1 Disposition of Subjects

Disposition summary will include tabulation of the number of the subjects who enrolled into the OLE (overall and by Cohort) as well as the number and percentage of subjects who received treatment during the OLE (overall and by Cohort), completed the OLE, prematurely discontinued during the OLE (including reasons for discontinuation and ET due to COVID-19 disruption) and in each analysis population by previous treatment group in parent studies as defined in Section 5. The percentages will be calculated using the number of subjects included in the full analysis population.

 Innovaderm Research	STATISTICAL ANALYSIS PLAN, Final Version 1.0
Protocol Number: ARQ-151-313	Sponsor: Arcutis Biotherapeutics, Inc.

Number of days in the study will be summarized with descriptive statistics by previous treatment group in parent studies as defined in Section 5. For each subject, the number of days in the study will be calculated as following:

$$\text{Date of completion/discontinuation} - \text{Date of enrollment into OLE} + 1$$

A listing of subject's disposition and inclusion/exclusion from analysis population will be provided.

7.2 Protocol Deviations

A data review will be conducted before the IA database lock as well as before the final database lock by the Medical Monitor and the Sponsor to classify protocol deviations as important or non-important. The number and percentage of subjects with at least one protocol deviation, at least one protocol deviation associated with COVID-19, and at least one important protocol deviation will be summarized by previous treatment group in parent studies based on the full analysis set. Protocol deviations associated with COVID-19 and important protocol deviations will be further broken down by deviation category.

A listing of all protocol deviations will also be provided. The protocol deviations associated with COVID-19 and important PDs will be flagged.

8 DEMOGRAPHIC AND BASELINE CHARACTERISTICS

Demographics and baseline characteristics will be summarized with descriptive statistics by previous treatment group in parent studies as defined in Section 5 using the safety population.

The list of demographics to be summarized includes:

- Age (years) at the start of the parent study
- Age group at the start of the parent study: 2 – 5 years, 6 – 11 years, 12 - 17 years, ≥ 18 years
- Age (years) at the start of the OLE study
- Age group at the start of the OLE study: 2 – 5 years, 6 – 11 years, 12 - 17 years, ≥ 18 years
- Sex at birth
- Childbearing potential at the start of the OLE study
- Race*

 Innovaderm Research	STATISTICAL ANALYSIS PLAN, Final Version 1.0
Protocol Number: ARQ-151-313	Sponsor: Arcutis Biotherapeutics, Inc.

- Ethnicity
- Fitzpatrick Skin Type
- Prior failure of Topical Corticosteroids, Topical Calcineurin Inhibitors, Eucrisa;
- Atopic Dermatitis involvement on the face, on the eyelids

The following efficacy assessments will be summarized at both Primary Baseline and OLE Baseline:

- Baseline vIGA-AD (continuous and categorical)
- Baseline WI-NRS
- Baseline BSA affected by AD (%)
- Baseline EASI total score
- Baseline SCORAD

The following assessments will be summarized at the Primary Baseline only:

- Baseline Height (cm)
- Baseline Weight (kg)
- Baseline Body Mass Index (BMI) (kg/m²) for children (2 – 5 years, 6 – 11 years), adolescents (12 – 17 years), and adult (\geq 18 years)
- Baseline DLQI/CDLQI/IDQOL
- Baseline DFI
- Baseline POEM
- Baseline PHQ-8
- Baseline PHQ-A
- Baseline CDI-2

*Subjects who reported more than one race will be summarized as 'Multiple' races in the table.
All races selected will be displayed in the listing.

A listing of all demographics and baseline characteristics will be provided.

 Innovaderm Research	STATISTICAL ANALYSIS PLAN, Final Version 1.0
Protocol Number: ARQ-151-313	Sponsor: Arcutis Biotherapeutics, Inc.

9 SURGICAL AND MEDICAL HISTORY

Surgical and medical history will be coded according to the Medical Dictionary for Regulatory Activities (MedDRA), Version 25.0 or higher. Medical and surgical history collected in the parent studies for subjects that rolled over into this study will be included and presented.

Surgical and medical history will be summarized by system organ class (SOC), preferred term (PT), and treatment group as defined in Section 5 using the safety population. A subject who experienced the same surgical and medical history event multiple times will be counted only once for the corresponding PT. Similarly, if a subject experienced multiple surgical and medical history events within the same SOC, the subject will be counted only once for that SOC. Surgical and medical history events will be sorted alphabetically by SOC and within each SOC the PT will be presented by descending frequency in the safety population.

10 PRIOR AND CONCOMITANT MEDICATIONS

Medications will be coded according to the World Health Organization Drug Dictionary (WHO-DD), March 2022 B3.

Prior medications are defined as any medication started and discontinued prior to the first study treatment dosing in the OLE. Concomitant medications are defined as any medication taken on or after the first dose of study treatment in OLE, including those who started prior to the first dose of study treatment date and continued past that date in OLE study. See [Appendix 2](#) for handling of completely or partially missing dates for prior and concomitant medications.

Incidence of concomitant medications will be tabulated by Anatomic Therapeutic Class (ATC) level 3, preferred drug name, and treatment group as defined in Section 5 using the safety population. A subject with the same medication taken multiple times will be counted only once for the corresponding preferred drug name. Similarly, if a subject has taken more than one medication within the same ATC level, then the subject will be counted only once for that ATC. Concomitant medications will be sorted alphabetically by ATC level and within each ATC level, the preferred drug name will be presented by descending order.

Prior medications are not planned to be listed and summarized in this study as prior medications were presented in parent studies.

A listing of concomitant medications will be provided.

 Innovaderm Research	STATISTICAL ANALYSIS PLAN, Final Version 1.0
Protocol Number: ARQ-151-313	Sponsor: Arcutis Biotherapeutics, Inc.

11 STUDY TREATMENT EXPOSURE AND TREATMENT COMPLIANCE

A summary of exposure to study treatment will be presented using the safety population by treatment group as defined in Section 5. It will include descriptive statistics on the number of days on OLE study treatment, as well as the number of study treatment applications based on diary, for each treatment group. Since subjects in the roflumilast arm of their parent study will simply be continuing the same treatment, their first treatment date will be the date of their week 4 visit in the parent study, even if study drug application was interrupted on that date. The number of days on study treatment in OLE study, will be calculated as follows:

$$(\text{Last treatment date in OLE} - \text{First treatment date in OLE}) + 1$$

For each subject, compliance (%) with study treatment will be calculated as follows:

$$\frac{\text{Number of study treatment applications}}{\text{Number of expected study treatment applications}} \times 100$$

Applied dose count and missed dose applications count were collected in eCRF study drug interruption module. Number of study treatment applications will be calculated as the sum of applied dose count.

Number of expected study treatment applications will be calculated as the sum of number of investigational product applications and number of doses missed. Of note, number of expected study treatment applications might change during the course of the study (refer to Section 3.1 for more details).

The number and percent of subjects who switch to a maintenance dosing schedule (BIW) at least once after week 4 will be provided by treatment group. The cumulative time and percent of time (Section 5.5) on the maintenance dosing schedule will be summarized only for those subjects who switched to BIW dosing at least once. The percent of time on the maintenance dosing schedule will also be summarized categorically as]0-25%],]25-50%],]50-75%], and >75%. The number of times each subject returned to QD dosing after switching to BIW dosing will be summarized categorically.

Subjects who roll over from the ARQ-151-315 study and turn 6 years old during the study will switch to Roflumilast cream 0.15% at their first scheduled post-birthday visit. The percentage of study days spent on each dose in this study will be summarized.

 Innovaderm Research ■■■	STATISTICAL ANALYSIS PLAN, Final Version 1.0
Protocol Number: ARQ-151-313	Sponsor: Arcutis Biotherapeutics, Inc.

Descriptive statistics for the number of missed applications as well as the number and percentage of subjects who missed more than 3 consecutive doses while on the QD dosing schedule or more than 2 consecutive doses while on the BIW dosing schedule will be presented by treatment group as defined in Section 5. Descriptive statistics for the compliance as well as number and percentage of subjects with < 80%, [80% - 100%], and >100% compliance will be presented similarly.

Furthermore, the number and percentage of subjects deemed as compliant with the dosing regimen, defined as subjects meeting both of the following requirements will also be provided by treatment group as defined in Section 5 using the safety population:

- Apply at least 80% of the expected applications during the study drug application period
- Do not miss more than 3 consecutive doses while on the QD dosing schedule or more than 2 consecutive doses while on the BIW dosing schedule.

Total weight of study treatment applied will be summarized by treatment group as defined in Section 5 using descriptive statistics in the safety population. Weight of study treatment used will be documented in source documents and in eCRF. Total weight of study treatment applied is determined by subtracting returned tube weight from the dispensed tube weight for each tube that was dispensed and summing the weights. Of note, if a tube lasts for more than 1 visit, the Dispensed Tube Weight is the last weight measured and not the full tube weight. If a tube is not returned at a specific visit, then weight will be considered as missing at that visit.

A listing of exposure to study treatment, compliance with study treatment, and total weight of study treatment applied will be provided. A listing of drug accountability including the kit number, tube number, dispensed and returned weight will also be provided.

12 EFFICACY ANALYSES

Unless otherwise indicated, missing efficacy data will not be imputed.

Efficacy endpoints will be summarized based on the full analysis set. For change and percent change efficacy endpoints relative to baseline, summaries will be performed relative to both Primary Baseline and OLE Baseline (refer to Section 5.2).

12.1 Primary Efficacy Endpoint

Not applicable.

 Innovaderm Research ■■■	STATISTICAL ANALYSIS PLAN, Final Version 1.0
Protocol Number: ARQ-151-313	Sponsor: Arcutis Biotherapeutics, Inc.

12.2 Secondary Efficacy Endpoints

The secondary efficacy endpoints are:

- vIGA-AD score of clear (0) or almost clear (1) at each assessment (refer to Section 5.5)
- vIGA-AD success (refer to Section 5.5) over time
- Change and percent change from baseline in WI-NRS over time
- Change and percent change from baseline in EASI total score (refer to Section 5.5) over time

These endpoints are based on the following scales/questionnaire:

- The vIGA-AD scale is a static evaluation of qualitative overall AD severity. This global assessment scale is an ordinal scale with five severity grades (reported only in integers of 0 to 4), where a higher score represents a greater severity. Each grade is defined by a distinct and clinically relevant morphologic description that minimizes inter-observer variability. vIGA-AD is evaluated for the entire body except the scalp, palms, and soles.
- The WI-NRS scale is a single-item assessment of the subject-reported worst itch severity during the previous 24-hour period. The scale is from 0 to 10 ('no itch' or 'worst itch imaginable'). The WI-NRS will be self-reported by subjects for subjects ≥ 6 years of age and reported by parent/guardian for subjects < 6 years of age.
- The EASI questionnaire assessed the severity of erythema, induration/infiltration (papules), excoriation, and lichenification, as seen on the day of the examination, of four anatomic sites separately (head, upper extremities, trunk, and lower extremities). The severity of each sign is assessed using a 4-point scale (half steps are allowed e.g., 0.5): 0 (none), 1 (mild), 2 (moderate), and 3 (severe). The area affected by AD within a given anatomic site is estimated as a percentage of the total area of that anatomic site and assigned a numerical value according to the degree of AD involvement as follows: 0 (no involvement), 1 (1-9%), 2 (10-29%), 3 (30-49%), 4 (50-69%), 5 (70-89%), and 6 (90-100%). The EASI total score is then computed as specified in Section 5.5.

12.2.1 Main Analysis

Missing vIGA-AD secondary efficacy endpoints will be imputed as described in Section 6.2.1. The combined common proportion of subjects achieving each vIGA-AD secondary endpoint will be provided by visit and treatment group (refer to Section 5) along with their combined common two-sided 95% CI. The vIGA-AD success summaries based on the OLE Baseline (refer to Section

 Innovaderm Research	STATISTICAL ANALYSIS PLAN, Final Version 1.0
Protocol Number: ARQ-151-313	Sponsor: Arcutis Biotherapeutics, Inc.

5.2) will only include subjects who have an OLE baseline score other than clear (0) or almost clear (1).

The change and percent change from baseline in WI-NRS score will be summarized among subjects 12 years or older at the start of the parent study* using descriptive statistics by visit and treatment group (refer to Section 5) based on observed cases (i.e., no imputation). Two-sided 95% CI of the mean will also be provided. WI-NRS score will be summarized similarly.

* WI-NRS score, change from baseline and percent change from baseline for subjects < 12 years old at the start of the parent study will be summarized in subgroup analysis (refer to Sections 6.6 and 12.2.3).

The change and percent change from baseline in EASI total score will be summarized using descriptive statistics by visit and treatment group (refer to Section 5) based on observed cases (i.e., no imputation). Two-sided 95% CI of the mean will also be provided. EASI total score will be summarized similarly.

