4 POPULATIONS FOR ANALYSIS

4.1 Full Analysis Population

The full analysis population is defined as all subjects who are enrolled in this study.

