5.2 Baseline

There are two baseline definitions for the analyses:

- Primary baseline is defined as the last observation before or on the first dose of roflumilast cream 0.15% or 0.05% in ARQ-151 parent studies for subjects administered roflumilast previously and before or on the first dose of roflumilast cream 0.15% or 0.05% in this study* for subjects administered vehicle previously.
- OLE baseline is defined as the last observation before or on the first dose of roflumilast cream 0.15% or 0.05%* in this study.

If the last non-missing assessment was performed on the same date as the first dose of roflumilast cream* and time is not available, the assessment will be considered as baseline, except for adverse events (AEs) and medications starting on the first dose date which will be considered post-baseline. For subject local tolerability assessments, if the last non-missing assessment was performed on the same date as the first dose of roflumilast cream*, the assessment will be considered as baseline, regardless of the time of the assessment.

For the subjects administered vehicle in the parent study, the definition for Primary and OLE baselines are the same.

* Enrollment date (usually the Week 4 visit in the parent study) for enrolled subjects who discontinued early from this study before the first application of roflumilast cream 0.15% or 0.05%.

The following table ([Table 2](#)) described the baseline used in the analysis:

 Innovaderm Research	STATISTICAL ANALYSIS PLAN, Final Version 1.0
Protocol Number: ARQ-151-313	Sponsor: Arcutis Biotherapeutics, Inc.

Table 2 Summary of Primary/OLE Baseline in the Analyses

Analyses	Baseline*
Demographics and Baseline Characteristics	Primary baseline and OLE baseline, as applicable
Efficacy Analysis	Primary baseline and OLE baseline
Safety analysis for AEs and concomitant medications	OLE baseline
Safety analysis for clinical laboratory, vital signs, local tolerability assessments. PHQ-8, Modified PHQ-A, CDI-2, C-SSRS, and physical examination	Primary baseline

* Refer to Section 8 for more details.

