5.5 Derived Variables

All questionnaire scores will be derived by Biostatistics in the ADaM datasets using the formulas defined below, even if calculated scores are present in the EDC database. All pre-calculated scores will be ignored for analysis.

- With the following exception, vIGA-AD Score of Clear (0) or Almost Clear (1) = vIGA-AD of ‘Clear’ (0) or ‘Almost Clear’ (1). The exception is that for subjects who discontinued early from study due to an AE or lack of efficacy, the subject will be considered as not having a vIGA-AD score of Clear (0) or Almost Clear (1) for all pre-specified analysis visits (refer to Section 5.4) for which the subject’s day of last dose falls within or is before the start of the analysis visit window.
- With the following exception, vIGA-AD Success = vIGA-AD of ‘Clear’ (0) or ‘Almost Clear’ (1) plus at least a 2-grade improvement from baseline. The exception is that for subjects who discontinued early from study due to an AE or lack of efficacy, the subject will be considered as not having a vIGA-AD success for all pre-specified analysis visits (refer to Section 5.4) for which the subject’s day of last dose falls within or is before the start of the analysis visit window. vIGA-AD Success will be derived for both the Primary and OLE baselines (refer to Section 5.2)
- Date of last contact = the latest of last study visit date, last dose date, end-of-study date and end-of-treatment date.
- Post-OLE Week 4 study duration (days): The duration can be represented as End Date – Start Date +1. The start date of the Post-OLE Week 4 interval will be the date of the OLE Week 4 visit or OLE Day 29 if the subject missed the OLE Week 4 visit. The end date will be the date of last contact. This endpoint will be calculated only for subjects who enter the post-OLE Week 4 study period.
- Duration (days) of the first BIW dosing will be calculated from the first BIW dosing to the start of the succeeding QD dosing interval. Subject’s last contact date will be used to censor

 Innovaderm Research	STATISTICAL ANALYSIS PLAN, Final Version 1.0
Protocol Number: ARQ-151-313	Sponsor: Arcutis Biotherapeutics, Inc.

this endpoint (time-to-event analysis) or as the end date of this duration (analyzed as a continuous endpoint) for subjects who do not revert to a QD dosing regimen after the first BIW dosing. This endpoint will be calculated only for subjects who enter the post-OLE Week 4 study period with at least one BIW dosing interval.

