12.2.2 Sensitivity Analyses

As sensitivity analyses to the imputation method used for the main analysis of the vIGA-AD endpoints (refer to Section 12.2.1), the main analysis of these endpoints will be repeated, but using the following imputation method:

- Non-responder imputation (refer to Section 6.2.2)
- Observed cases (i.e., no imputation)

No sensitivity analyses will be performed for the secondary efficacy endpoints based on WI-NRS and EASI total score.

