12.2.3 Subgroup Analyses

The main analysis of the secondary efficacy endpoints of vIGA-AD score of clear (0) or almost clear (1) and vIGA-AD success (refer to Section 12.2.1) will be repeated for each of the subgroups mentioned in Section 6.6. Subgroup analyses will only be conducted for results relative to the primary baseline only.

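### vIGA-AD success: vehicle roll-overs entering at 0/1 are dropped from the OLE-Baseline summaries but count as unavoidable non-successes in the Primary-Baseline ones, although the two baselines are the same score for them

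*SAP*

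**What the plan says.** SAP 5.5 defines vIGA-AD success as a score of 0 or 1 "plus at least a 2-grade improvement from baseline", and adds that "vIGA-AD Success will be derived for both the Primary and OLE baselines". SAP 5.2 sets the Primary Baseline at the first roflumilast dose in either study and the OLE Baseline at the first dose in this study. It then notes: "For the subjects administered vehicle in the parent study, the definition for Primary and OLE baselines are the same".

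SAP 12.2.1 says that the success summaries on the OLE Baseline "will only include subjects who have an OLE baseline score other than clear (0) or almost clear (1". It gives no matching condition for the Primary-Baseline summaries, so the general rules apply to those: "Efficacy endpoints will be summarized based on the full analysis set" (SAP 12), and "The full analysis population is defined as all subjects who are enrolled in this study" (SAP 4.1).

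Two further provisions matter. For the sensitivity analyses, "the main analysis of these endpoints will be repeated, but using the following imputation method" (SAP 12.2.2), the methods being non-responder imputation and observed cases. For subgroups, "Subgroup analyses will only be conducted for results relative to the primary baseline only" (SAP 12.2.3).

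**The concern.** The SAP accepts, for the OLE Baseline, that a subject already clear or almost clear does not belong in a success denominator. For vehicle roll-overs the same score is also the Primary Baseline, but there these subjects remain. One group, with one baseline score and one endpoint, therefore gets two success rates that differ only through the denominator rule. A vehicle roll-over who enters clear and stays clear throughout is shown as a non-success in the Primary-Baseline table.

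The roflumilast column does not have this feature. Its Primary Baseline is the parent-study score, for which SAP 6.6 lists only 2 and 3. The pooled column therefore mixes subjects who can all succeed with some who cannot. In the subgroup tables, if the share entering at 0/1 differs between subgroups, part of any difference in success would come from the denominator and not from response.

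**Working it through.** The documents state no success rate or precision figure for this endpoint, so there is no planned number to reproduce.

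**Can a subject at 0/1 succeed?** The scale is the integers 0 to 4 (SAP 12.2). Applying the SAP 5.5 definition to each baseline score gives these qualifying later scores: from 0, none; from 1, none; from 2, only 0; from 3, 0 or 1; from 4, 0 or 1. Imputation cannot alter this, because SAP 6.2.1 keeps imputed scores within the scale and SAP 6.2.2 sets missing endpoints to non-response.

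**Can such subjects be enrolled?** Protocol 4.5.1 requires completion of the parent study through Week 4, and neither 4.5.1 nor 4.5.2 sets a minimum vIGA-AD. SAP 6.6 plans a subgroup of subjects at 0 at OLE baseline; it is not specific to vehicle, but nothing keeps vehicle subjects out of it.

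**Symbols, all for one visit's denominator.** p0 = share of vehicle subjects who entered at 0/1; s = success among the other vehicle subjects; r = success among roflumilast roll-overs; v = vehicle share of the pool. The documents give none of these, so every value below is assumed.

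**Main analysis.**
- Vehicle column: as written s × (1 - p0); restricted to baseline 2 or higher, s. Ratio (1 - p0).
- Pooled column: as written (1 - v) × r + v × (1 - p0) × s; restricted, the same numerator divided by (1 - v × p0). Ratio (1 - v × p0), whatever r and s are.

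In the table the restricted rate is the p0 = 0% row of each column. The pooled columns take r = s = 50%.

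| p0 | Vehicle, s = 40% | Vehicle, s = 50% | Vehicle, s = 60% | Pooled, v = 1/3 | Pooled, v = 1/2 |
|---|---|---|---|---|---|
| 0% | 40% | 50% | 60% | 50% | 50% |
| 5% | 38% | 47.5% | 57% | 49.2% | 48.8% |
| 10% | 36% | 45% | 54% | 48.3% | 47.5% |
| 20% | 32% | 40% | 48% | 46.7% | 45.0% |
| 30% | 28% | 35% | 42% | 45.0% | 42.5% |

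**Check with counts (assumed).** Take 600 roflumilast subjects at 55% (330 successes) and 240 vehicle subjects at 2 or higher at 45% (108 successes). Restricted pooled rate: 438/840 = 52.1%. Add 60 vehicle subjects at 0/1: 438/900 = 48.7%. The ratio is 840/900 = 0.933, which equals 1 - (1/3) × 0.2.

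**Subgroups.** In the vehicle column with s = 50% in both of two subgroups, p0 of 10% in each gives no gap. At 10% against 20% the rates are 45% and 40%, a gap of 5 points; at 10% against 30% they are 45% and 35%, a gap of 10 points.

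**Which denominator.** SAP 6.2.1 sets imputed Week 36 and Week 52 values to missing for Cohort-Week 24, so p0 and v at those visits are not the shares among all enrolled subjects. In the observed-cases analysis, a subject with a missing visit leaves the denominator at that visit; a 0/1 entrant counts as a non-success only where observed.

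**What can be recovered.** The restricted vehicle rate already appears in the OLE-Baseline table. The restricted pooled point estimate is the n-weighted average of the roflumilast Primary-Baseline and vehicle OLE-Baseline columns, given that SAP 6.2.1 expects no missing OLE Day 1 scores. The pooled CI does not follow from those columns. The success subgroup tables have no OLE-Baseline counterpart, and SAP 8 tabulates baseline vIGA-AD by previous treatment, not by subgroup. SAP 8 also promises a baseline listing, from which the 0/1 subjects could be counted.

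**The case against.** The strongest reply is that the unrestricted Primary-Baseline rate is what the protocol asks for. Protocol 3.2.2 defines success with no condition on the baseline score, and Protocol 4.3 takes baseline as the last observation before the first ARQ-151 dose in either study, which is the SAP's Primary Baseline. The restricted OLE-Baseline table is an addition, and two summaries with different declared denominators may properly give two rates. This stands. A reader might infer that the Primary-Baseline rate is an error or departs from the protocol and should be replaced; the documents do not support that. What remains is that the table does not show how many subjects in it cannot succeed.

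A second reply is that the rule in SAP 12.2.1 reaches vehicle subjects anyway, since their Primary Baseline is their OLE Baseline. The sentence is tied to the OLE-Baseline summaries, so if more was meant, the text still needs to say so.

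A third is that restriction selects vehicle subjects who were still at 2 or higher after four weeks of vehicle. That is true, and is a reason to add the restricted rate and not to substitute it. It does not make the vehicle and roflumilast columns comparable.

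Three other stronger readings also fail. The affected denominators are not all enrolled subjects at every visit, because of Cohort-Week 24 and the observed-cases rule. The subgroup information is not lost, because the baseline listing allows a count; what is missing is a ready-made table and CI. And it cannot be said that success is understated by any known amount, because p0 may be zero.

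**Conclusion.** The point holds as a minor one. Vehicle roll-overs entering at 0/1 cannot meet the success criterion, yet they lower the Primary-Baseline vehicle, pooled and subgroup success rates wherever they are in the visit's denominator. That they are in it follows from the general analysis-set rule and the absence of an exclusion; the SAP does not say so in words.

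In the main analysis the factors (1 - p0) and (1 - v × p0) are exact for any success rates, provided OLE Day 1 scores are complete, as the SAP expects. The size in points rests wholly on assumed inputs. Over p0 from 0% to 30% with 50% success among the others, the vehicle column loses 0 to 15 points; with roflumilast success also at 50%, the pooled column loses 0 to 5 points at v = 1/3 and 0 to 7.5 points at v = 1/2.

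No trial conclusion changes. The primary endpoints are safety, success is a descriptive secondary endpoint, SAP 5.7 plans no hypothesis tests, and the companion endpoint of a score of 0 or 1 is unaffected.

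**What to change.** In SAP 12.2.1 and 12.2.3, keep the all-enrolled Primary-Baseline success rate and add beside it, in the main, sensitivity and subgroup tables, the rate and 95% CI among subjects with vIGA-AD of 2 or higher at Primary Baseline. Report the number at 0/1 at Primary Baseline per column and per subgroup, counted in each visit's denominator. Footnote two things: these subjects cannot meet the success criterion; and the restricted vehicle column is selected for non-response to vehicle, so it is not directly comparable with the roflumilast column. Record the addition in SAP 3.6. Leave the baseline definitions in SAP 5.2 as they are.

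The cost is a denominator flag, extra table rows, a footnote and the SAP 3.6 entry; no new data are needed. The added rate has a smaller, selected denominator: on the assumptions above, 0% to 30% fewer vehicle subjects and, since v × p0 is at most 1/2 × 30%, 0% to 15% fewer in the pooled column. In the main table the restricted vehicle rate will repeat the OLE-Baseline one; the real gain is in the pooled CI and the subgroup tables.
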